1.3 STUDY RATIONALE AND BENEFIT-RISK ASSESSMENT

This open-label extension–safety monitoring (OLE-SM) study consists of two parts.

1.3.1 Study Rationale for Part 1 (Open-Label Extension or “OLE”)

Part 1 (OLE) of this study is designed to assess the long-term safety and tolerability of 105 mg SC etrolizumab every four weeks with regard to adverse events and laboratory abnormalities and to obtain long-term data on the efficacy and immunogenicity.

Patients receiving etrolizumab or placebo in Study GA29144 may be eligible to participate and will receive etrolizumab in Part 1 (OLE) of this study. Eligibility criteria and the timepoints for enrollment into the Part 1 (OLE) of this study are described in Section [4.1.1](#).

1.3.2 Study Rationale for Part 2 (Safety Monitoring or “SM”)

Part 2 (SM) of this study is designed to monitor for PML in patients who have stopped taking etrolizumab. Patients who exit Part 1 (OLE) of this study will then enter Part 2 (SM) of this study for monitoring for events of PML. In addition, all patients from Study GA29144 who do not enroll in Part 1 (OLE) of this study for continued etrolizumab treatment will be asked to enroll directly into Part 2 (SM) of this study for extended PML safety monitoring (following completion of the 12-week safety follow-up in Study GA29144).

1.3.3 Benefit-Risk Assessment

The current therapeutic options available for CD include corticosteroids, immunosuppressants, and biological agents. These treatments reduce symptoms and improve quality of life; however, patients often stop responding to treatments and the goals of maintaining clinical remission and healing mucosal inflammation are not achieved. Moreover, these therapies are associated with adverse effects including diabetes (reported with corticosteroid use; Peyrin-Boulet et al. 2010), systemic toxicities such as leucopenia and thrombocytopenia (reported with immunosuppressant use; Prefontaine et al. 2009), and an increased risk for lymphoma and serious and opportunistic infections (reported with immunosuppressant and anti-TNF use when given as monotherapy or in combination; Siegal and Melmed 2009).

The anti-integrins are another class of biologics approved for the treatment of CD. The reported efficacy of the recently licensed anti-integrin vedolizumab, an intravenously administered anti- $\alpha4\beta7$ mAb, in CD demonstrates a role for $\alpha4\beta7$ in the pathobiology of this disease (Sandborn et al. 2013). In addition to demonstrating efficacy compared with placebo, vedolizumab had an acceptable safety profile in two Phase III trials for CD (Sandborn et al. 2013; Sands et al. 2014). Although long-term safety data for vedolizumab are still being collected, to date no cases of PML *attributed to vedolizumab* have been reported.

Similar to vedolizumab, etrolizumab is a gut-selective anti-integrin, which blocks homing of leukocyte subpopulations to the intestinal mucosa by blocking $\alpha 4\beta 7$ integrin (see Etrolizumab Investigator's Brochure). In addition, etrolizumab may interfere with pathologic lymphocyte retention along the mucosa by blocking the interaction between $\alpha E\beta 7$ and E-cadherin. Etrolizumab showed significant rates of remission at 10 weeks in treating moderately to severely active UC when compared with placebo in the Phase II Study ABS4986g (EUCALYPTUS study; Vermeire et al. 2014) and was associated with ongoing high rates of clinical response among 108 of 124 patients from EUCALYPTUS who received open-label etrolizumab after roll-over into the Phase II OLE SPRUCE study (Study GA27927).

The most recent SPRUCE data cut (June 2014) demonstrates the median exposure to etrolizumab was 7.29 months, with 51% of patients experiencing at least 7–11 months of exposure and 11% experiencing at least 24 months. In most cases, this duration of exposure to etrolizumab is in addition to 10 weeks of treatment with etrolizumab in the EUCALYPTUS study. At the time of the data cut in this ongoing study, 80% of patients in SPRUCE experienced adverse events and 15% experienced at least one serious adverse event. The most common adverse events were nasopharyngitis (occurring in 25% of patients), UC flare (23.1%), headache (12%), arthralgia, gastroenteritis, and upper respiratory tract infection (11.1% each).

A potential safety risk associated with the use of anti-integrins includes the risk for infections related to gut-selective treatment blockade of lymphocyte trafficking and the potential for suppression of host defense against infectious pathogens. However, an analysis of the EUCALYPTUS study showed that infection rates were similar between etrolizumab and placebo in the subgroups of patients taking concomitant immunosuppressant therapy and the subgroups not taking this concomitant treatment (see Etrolizumab Investigator's Brochure). A slightly higher rate of infection was observed during long-term exposure to etrolizumab in SPRUCE compared with EUCALYPTUS, but only 3 patients have discontinued from SPRUCE to date because of infection-related adverse events (see Etrolizumab Investigator's Brochure).

Although the efficacy of etrolizumab has not been studied in patients with CD, preliminary expression studies of the pharmacological target for etrolizumab, the integrin $\beta 7$ receptor on gut CD4+ and CD8+ T cells isolated from resections of patients with UC and patients with CD, show that expression levels are similar between both diseases. In addition, because αE expression is reportedly elevated in patients with CD (Elewaut et al. 1998; Oshitani et al. 2003), with an observed increase in expression from distal to proximal bowel, etrolizumab may bring enhanced efficacy in CD. Given the preliminary evidence of efficacy in patients with UC and that elements of pathogenesis are shared across UC and CD, etrolizumab has the potential to be a novel, effective treatment for CD and will be assessed as a treatment for patients who are TNF-naive and patients who are non-responsive or refractory to anti-TNF therapy

(TNF-IR) with moderately to severely active CD in the combined Phase III, randomized, placebo-controlled induction and maintenance studies, Study GA29144.

Patients who experience disease worsening that is confirmed at Week 10 in the Induction Phase of Study GA29144 will have the option of enrolling in Part 1 (OLE) of Study GA29145 between and including Weeks 10 and 14 of the Induction Phase. Patients who are not eligible for the Maintenance Phase may also have the option to enroll in Part 1 (OLE) of Study GA29145, if eligible. During the Maintenance Phase in Study GA29144, patients will be able to withdraw and enter Part 1 (OLE) if they experience a clinical relapse (as defined in Section 4.1.1).

Study GA29144 patients who experience disease progression or lack of response while assigned to placebo during either the Induction or Maintenance Phase are expected to benefit most from participation in Part 1 (OLE) of Study GA29145. Patients who experienced disease progression or lack of response while assigned to etrolizumab in Study GA29144 may also experience treatment benefit by participating in Part 1 (OLE) depending on severity of disease and available treatment options, which include anticipated treatment benefit from rescue medication. Consequently, eligible patients from Study GA29144 are encouraged to enroll in Part 1 (OLE) to receive open-label etrolizumab with rescue medications at the discretion of the investigator, including the use of concomitant immunosuppressant therapy.

Patients may enter Part 1 (OLE) between Weeks 10 and 14 in Study GA29144, having received an induction regimen of either 210 mg or 105 mg etrolizumab. Data from the SPRUCE OLE study, in which patients received either 100 mg etrolizumab every 4 weeks (Q4W) or 300 mg etrolizumab Q4W (followed by a protocol-amendment driven reduction to 100 mg etrolizumab Q4W) after administration of placebo, 100 mg etrolizumab, or 300 mg etrolizumab (both are nominal doses) in the EUCALYPTUS Phase II study, showed that response and remission rates in SPRUCE were similar when the results were analyzed by treatment received in EUCALYPTUS. The clinical response rates in SPRUCE at Week 4, for patients previously treated with 100 mg etrolizumab, 300 mg etrolizumab, or placebo, were 48%, 49%, and 53%, respectively (n=31–38; see Etrolizumab Investigator's Brochure). Among TNF-IR patients, clinical response rates in SPRUCE at Week 4, for patients previously treated with 100 mg etrolizumab, 300 mg etrolizumab, or placebo, were 42%, 50%, and 44%, respectively (n=8–12). Given that both induction doses (105 mg and 210 mg) in Study GA29144 are expected to achieve full $\beta 7$ receptor occupancy and assuming that receptor occupancy is required for efficacy, these data suggest that patients who enter Part 1 (OLE) from the 210 mg arm of the Induction Phase of Study GA29144 may experience a treatment benefit with longer etrolizumab treatment. As described earlier, permitted use of corticosteroid and immunosuppressant therapy with etrolizumab in the OLE may benefit all patients escaping from Study GA29144 because of disease worsening. Safety events will be carefully and regularly monitored while patients are taking etrolizumab in Part 1 (OLE) and for 2 years after their last dose of etrolizumab (12-week

safety follow-up plus 92-week PML safety monitoring). The investigator will review patient safety in Part 1 (OLE) every month for the first 3 months and then every 3 months thereafter until a patient completes the study or withdraws. Safety assessments will include: assessment of vital signs, safety laboratory results, neurological exams, and continuous review of adverse events. Pregnancy, development of anaphylaxis, PML, malignancy, colonic mucosal dysplasia, or certain specific serious infections (see Section 5) will lead to permanent discontinuation from etrolizumab treatment. In addition, after treatment of etrolizumab has stopped, patients will be followed for 12 weeks for all safety events and then 92 weeks for any signs and symptoms of PML. Patients will be carefully monitored for symptoms of PML through regular neurological examinations and with the use of the PML subjective and objective checklists (Section 4.4.4.5)

In summary, there is a strong rationale and a positive benefit-risk assessment for studying etrolizumab in Crohn's Disease. Safety and efficacy results from the UC OLE SPRUCE study suggest that etrolizumab has an acceptable clinical safety profile and could benefit patients who are eligible to receive long-term treatment after exiting Study GA29144.

1.3.4 Rationale for Test Product Dosage

Patients enrolling in Part 1 (OLE) of this open-label extension–safety monitoring (OLE–SM) study from Study GA29144 will receive a dose of 105 mg of etrolizumab. A dosing regimen of 105 mg SC Q4W is specified in Part 1 (OLE) on the basis of the following considerations:

- The 105-mg SC Q4W dose planned for the Phase III study in CD is anticipated (by population modeling) to maintain full $\beta 7$ –receptor occupancy at all times in > 85% of patients. The nominal dose of 100 mg SC Q4W administered in the UC Phase II study demonstrated an acceptable safety profile.
- The in-class anti-integrin vedolizumab was successful in maintaining remission with an every 8-week regimen that provided an average steady-state trough serum concentration sufficient to maintain maximal receptor occupancy (Rosario et al. 2013; Sandborn et al. 2013).

Of note, no etrolizumab will be administered during Part 2 (SM) of this OLE–SM study.

2. OBJECTIVES

2.1 OBJECTIVES OF THE STUDY

The objectives of this OLE-SM study are as follows:

Part 1 (OLE)

- To assess the long-term safety and efficacy of etrolizumab in patients eligible for Part 1 (OLE)

Part 2 (SM)

- PML safety monitoring in patients who have stopped study treatment

2.2 OTHER SAFETY OBJECTIVES

The other safety objectives for this study are as follows:

Part 1 (OLE)

- To evaluate the incidence, rate per subject-year, and severity of infection-related adverse events
- To evaluate the incidence and rate per subject-year of malignancies
- To evaluate the incidence and severity of hypersensitivity reactions
- To evaluate the incidence and the clinical significance of anti-therapeutic antibodies (ATAs)

2.3 EXPLORATORY OBJECTIVE OF THE STUDY

The exploratory objective for this study is as follows:

Part 1 (OLE)

- To assess endoscopic appearance at Week 108

3. STUDY DESIGN

3.1 DESCRIPTION OF STUDY

3.1.1 Overview of Study Design

This OLE-SM study is composed of two parts:

- Part 1 is the OLE for eligible patients, during which etrolizumab, 105 mg SC, will be administered Q4W followed by a 12-week safety follow-up post-treatment.
- Part 2 is the 92-week PML SM for all patients, during which no etrolizumab will be administered.

Patients who are enrolled in Part 1 (OLE) should participate in Part 2 (SM).

There may be patients from Study GA29144 who are ineligible for or choose not to participate in Part 1 (OLE) who will be asked to directly enroll in Part 2 (SM).

3.1.2 Overview of Part 1 (OLE)

Part 1 (OLE) of this study is an open-label, multicenter study to evaluate the long-term efficacy and safety of etrolizumab in patients with moderate to severe CD who were enrolled in Study GA29144 and who meet the eligibility criteria for enrollment into Part 1 (OLE; see Section 4.1.1).

All patients in Part 1 (OLE) will receive 105 mg etrolizumab Q4W by the SC route. All patients will be required to receive their first four doses (Weeks 0, 4, 8, and 12) of etrolizumab in the clinic setting as described in Section 4.2.2. Following the first four doses, etrolizumab may be administered in the home setting, and patients may self-administer the dose or have a caregiver administer the dose after being trained at the study clinic (see Section 4.2.2). If necessary, patients or their health care professional (HCP) may choose to continue administration of etrolizumab in the clinic.

Throughout Part 1 (OLE), patients will be monitored for safety by collection of safety parameters such as vital signs, laboratory tests, and adverse events (both serious and non-serious) and will be monitored for symptoms of PML with use of the PML subjective and objective checklists. Efficacy data will be evaluated by CDAI score, patient reported stool frequency (SF), and abdominal pain (AP) scores every 12 weeks until safety follow-up. In addition, patient's scoring on the abdominal pain questionnaire on an 11-point scale will be evaluated (see Appendix 6). Patients will have in-clinic visits at Weeks 0, 4, 8, and 12 and every 12 weeks thereafter (see Figure 1 and Appendix 1) and can continue to receive open-label etrolizumab in Part 1 (OLE) until commercial availability in their country or up to *approximately 10* years after the first patient is enrolled (see Section 3.2), whichever is earlier, or until the Sponsor's decision to terminate the study. Upon the completion of Part 1 (OLE) or early withdrawal from Part 1 (OLE), all patients will enter a 12-week safety follow-up, which consists of a telephone visit at Week 6 and an in-clinic visit at Week 12 (see Appendix 2).

During Part 1 (OLE), patients who have worsening CD may receive corticosteroid concomitantly (IV, oral, or topical) at the discretion of the investigator (see Section 4.3.1). Patients may continue immunosuppressant therapy (i.e., AZA, 6-MP, or MTX) with dose changes or initiate immunosuppressant therapy, at the discretion of the investigator (see Section 4.3.1). Any patient taking a prohibited therapy (described in Section 4.3.2) must withdraw from Part 1 (OLE), discontinue etrolizumab, and complete the 12-week safety follow-up, and then enter Part 2 (SM).

Upon completion of the 12-week safety follow-up, patients will enter Part 2 (SM) of the study, which will consist of 92 weeks of extended PML monitoring. See Figure 1 and Figure 2 for schemas of the study and see Section 3.1.3.

3.1.3 Overview of Part 2 (SM)

[figure not shown]
Patients may enroll into Part 2 (SM) of this study for 92 weeks of PML monitoring via two routes:

- Patients exiting Part 1 (OLE)
- Patients from Study GA29144 who are not eligible or choose not to receive etrolizumab in this study (e.g., due to receipt of prohibited medication)

Regardless of route of entry, patients will enroll following completion of the 12-week safety follow-up period within Part 1 of this study (OLE; for those entering from OLE) or within Study GA29144 (for those enrolling directly from Study GA29144).

[figure not shown]
During Part 2 (SM), patients will be assessed for PML and safety events via telephone visits at Weeks 24, 48, 68, and 92 (see [Figure 2](#) and [Appendix 3](#)). If there are any signs or symptoms suggestive of PML during the telephone visit, the patient will be asked to come into the clinic for a neurologic examination (see Section [4.4.5](#)).

Figure 1 Study Schema for Part 1 (Open-Label Extension; OLE) of the OLE-SM Study

OLE = open-label extension; OLE-SM = open-label extension—safety monitoring; Q4W = every 4 weeks; Q12W = every 12 weeks; SC = subcutaneous.

Figure 2 Study Schema for Part 2 (Safety Monitoring; SM) of the OLE-SM Study

OLE=open-label extension; OLE-SM=open-label extension–safety monitoring; PML=progressive multifocal leukoencephalopathy; ~Q24W=approximately every 24 weeks.

3.1.4 Number of Patients

The OLE-SM study will be conducted in investigational sites that have participated in Study GA29144. The maximum number of patients potentially enrolling in this study will be all patients from Study GA29144, approximately 1150 patients.

3.2 STUDY DURATION

Part 1 (OLE)

Part 1 (OLE) of this study will continue for up to *approximately 10* years after the first patient is enrolled into the study, until commercial availability, or until the Sponsor's decision to terminate the study, *whichever is earlier*. Patients who withdraw from Part 1 (OLE) will complete the 12-week safety follow-up and then enter Part 2 (SM) for PML monitoring.

Part 2 (SM)

For patients who enter Part 2 (SM) of this study either from Part 1 (OLE) or enroll directly from Study GA29144, Part 2 (SM) of the study will last 92 weeks.

3.2.1 End of Study

The end of the study is defined as the date when the last patient completes the 92-week PML safety-monitoring period.

3.3 OUTCOME MEASURES

The efficacy outcome definitions are given in [Table 1](#).

3.3.1 Efficacy Outcome Measures (Part 1; OLE)

The efficacy outcome measures for this study are as follows:

- CDAI remission assessed at 12-week intervals during Part 1 (OLE)
- Clinical remission assessed at 12-week intervals during Part 1 (OLE), as defined by a SF mean daily score ≤ 3 and an AP mean daily score ≤ 1 with no worsening in either subscore compared to baseline, averaged over 7 days prior to visit
- Simple Endoscopic Score for Crohn's disease (SES-CD) score assessed at Week 108 or at early withdrawal, if prior to Week 108, during Part 1 (OLE)

Table 1 Efficacy Outcome Definitions

Outcome Term	Definition
CDAI	CDAI is a composite of eight assessments: number of liquid or soft stools, abdominal pain, general well-being, presence of complications, taking Lomotil® (diphenoxylate/atropine) or other opiates for diarrhea, presence of an abdominal mass, hematocrit, and percentage deviation from standard weight
SES-CD	SES-CD is an endoscopic score derived from four variables (ulcers, ulcerated surface, inflamed surface, and presence of narrowing) that are scored in five ileocolonic segments.
CDAI Remission	CDAI score < 150
Clinical Remission	An SF mean daily score ≤3 and an AP mean daily score ≤1 with no worsening in either subscore compared to baseline, where the average is taken over 7 days prior to visit

AP = abdominal pain; CDAI = Crohn's Disease Activity Index; SES-CD = Simple Endoscopic Score for Crohn's disease; SF = liquid/soft stool frequency.

3.3.2 Safety Outcome Measures (Part 1; OLE)

The safety outcome measures for Part 1 (OLE) of this study are as follows:

- Incidence and severity of adverse events
- Incidence of serious adverse events
- Incidence, rate per subject-year, and severity of infection-related adverse events
- Incidence of serious infection-related adverse events
- Incidence and severity of injection-site reactions
- Incidence of adverse events leading to etrolizumab discontinuation
- Incidence of laboratory abnormalities
- Incidence and rate per subject-year of malignancies
- Incidence of ATAs to etrolizumab
- Incidence and severity of hypersensitivity reactions

3.3.3 Safety Outcome Measure (Part 2; SM)

The safety outcome measure for Part 2 (SM) of this study is as follows:

- Incidence of suspected or confirmed PML events

3.3.4 Exploratory Outcome Measures (Part 1; OLE)

The exploratory outcome measures for Part 1 (OLE) of this study are as follows:

- SES-CD ≤ 4 (≤ 2 for ileal patients), with no segment having a subcategory score (i.e., for ulceration size and extent, affected surface, or narrowing) that is >1 , at Week 108
- Change in SES-CD score between Week 0 (Study GA29144) and Week 108 or early withdrawal (Study GA29145, Part 1; OLE)

4. MATERIALS AND METHODS

4.1 PATIENTS

Part 1 (OLE)

The study population will consist of patients from Study GA29144 who meet all of the eligibility criteria for Part 1 (OLE) listed in Section 4.1.1.

Part 2 (SM)

The study population will consist of patients from Study GA29144 who either do not meet the eligibility criteria for Part 1 (OLE) or choose not to enroll in Part 1 (OLE) and patients from Study GA29145 who either completed or discontinued Part 1 (OLE), and who meet all the eligibility criteria for Part 2 (SM) listed in Section 4.1.1.

4.1.1 Inclusion Criteria

Part 1 (OLE)

- Patients who were previously enrolled in Study GA29144 and experienced any of the following:

Disease worsening in the Induction Phase of Study GA29144, defined as a CDAI score at Week 10 or later in the Induction Phase being greater than the patient's baseline (Week 0) score

Not eligible for the Maintenance Phase in Study GA29144

Completed the Week 14 visit in Study GA29144 and could not subsequently enter the Maintenance Phase, because the sample size for the Maintenance Phase has been achieved

A clinical relapse during the Maintenance Phase of Study GA29144, defined as meeting at least one of the following criteria on two consecutive visits (may include unscheduled visits), with at least one of the two consecutive CDAI scores ≥ 220 :

CDAI score \geq the baseline (Week 0) score

CDAI score ≥ 100 points higher than the Week 14 score

Completed the Maintenance Phase including the Week 66 or Week 74 clinic visit in Study GA29144

- Ability and willingness to provide written informed consent and comply with the requirements of the OLE-SM protocol.
- For women who are not postmenopausal (at least 12 months of non-therapy-induced amenorrhea) or surgically sterile (absence of ovaries and/or uterus): agreement to remain abstinent or to use a highly effective method of contraception (e.g., combined oral contraceptive pill or transdermal patch, spermicide and barrier [condoms], intrauterine device, implants for contraception, injections for contraception [with prolonged release], hormonal vaginal device, sterilization, or surgical tubal ligation) during the treatment period and for at least 24 weeks after the last dose of study drug (see [Appendix 4](#)).

Abstinence is acceptable only if it is in line with the preferred and usual lifestyle of the patient. Periodic abstinence (e.g., calendar, ovulation, symptothermal, or postovulation methods) and withdrawal are not acceptable methods of contraception.

- For men: agreement to remain abstinent or to use a condom, as well as not donate sperm, during the treatment period and for at least 24 weeks after the last dose of study drug

Abstinence is acceptable only if it is in line with the preferred and usual lifestyle of the patient. Periodic abstinence (e.g., calendar, ovulation, symptothermal, or postovulation methods) and withdrawal are not acceptable methods of contraception.

PART 2 (SM)

- Patients who participated in Study GA29144 and are not eligible or chose not to enroll in Part 1 (OLE)
- Patients who participated in Part 1 (OLE) of this protocol
- Ability and willingness to provide written informed consent and comply with the requirements of Part 2 (SM) of the OLE-SM protocol

All patients must have completed the 12-week safety follow-up in either GA29144 or GA29145, Part 1 (OLE), as applicable, prior to entering Part 2 (SM).

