- Patients who participated in Part 1 (OLE) of this protocol
- Ability and willingness to provide written informed consent and comply with the requirements of Part 2 (SM) of the OLE-SM protocol

All patients must have completed the 12-week safety follow-up in either GA29144 or GA29145, Part 1 (OLE), as applicable, prior to entering Part 2 (SM).

Exclusion Criteria

Patients who meet any of the following criteria will be excluded from study entry:

Part 1 (OLE)

- Patients who leave Study GA29144 before Week 10
- Patients who discontinue study drug in the Induction Phase of Study GA29144, except for those escaping between and including Weeks 10 and 14 due to disease worsening
- Inability to comply with the study protocol, in the opinion of the investigator
- Pregnancy or lactation
- Patients who developed an anaphylactic/anaphylactoid or severe allergic reaction to study medication during Study GA29144
- Patients who have an untreated or unresolved serious infection event
- Patients who experienced a de novo or reactivated serious viral infection such as hepatitis B virus (HBV), hepatitis C virus (HCV), or HIV during Study GA29144
- Patients who developed cytomegalovirus (CMV) colitis leading to early treatment discontinuation during Study GA29144
- Patients who developed life-threatening infections during Study GA29144
- Patients who developed a malignancy (with the exception of local and resected basal or squamous cell carcinoma of the skin) or who develop adenocarcinoma in situ (AIS), high-grade squamous intraepithelial lesions (HSIL), or cervical intraepithelial neoplasia (CIN) of Grade > 1 on cervical Pap smear or who develop colonic dysplasia during Study GA29144
- Receipt of the following prohibited medications since commencement of Study GA29144:
 - Any investigational treatment, including investigational vaccines
 - Use of T or B cell depleting agents (e.g., rituximab, alemtuzumab, or visilizumab), with the exception of azathioprine (AZA) and 6-mercaptopurine (6-MP), or equivalent
 - Use of cyclosporine, tacrolimus, sirolimus, or mycophenolate mofetil (MMF)
 - Use of natalizumab or vedolizumab
 - Use of TNF antagonists
 - Use of antagonists of IL-12 ± IL-23 (e.g., ustekinumab)*
 - Immunization with a live/attenuated vaccine
 - Use of anti-adhesion molecules (e.g., anti-MAdCAM-1)

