4.4.3 Assessments at Early Withdrawal

Part 1 (OLE)

Discontinuation during the OLE

Patients who discontinue treatment for any reason will be asked to complete the early withdrawal from treatment visit for Part 1 (OLE; see [Appendix 1](#)). The early withdrawal from treatment visit will be followed by a 12-week safety follow-up consisting of one telephone visit at Week 6 and one clinic visit at Week 12 (see [Appendix 2](#)). The patient should then enter the extended PML monitoring in Part 2 (SM; see [Appendix 3](#)).

Discontinuation during the 12-Week Safety Follow-Up Period after OLE

Patients who discontinue the study during the 12-week safety follow-up will be asked to complete the early withdrawal visit from the 12-week safety follow-up (see [Appendix 2](#)) and then enter the extended PML monitoring in Part 2 (SM).

Part 2 (SM)

Discontinuation during the Extended PML Monitoring Period of SM

Patients who discontinue from Part 2 (SM) of this study prior to completion of the extended PML monitoring period will be asked to complete the early termination visit from the extended PML monitoring period (see [Appendix 3](#)).

After the study completion/early termination visit, adverse events should be followed as outlined in Section [5.7](#).

See [Appendix 3](#) for specified follow-up assessments.

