	
 • Previously enrolled in Study GA29144 • Starting at Week 10, CDAI > patient's baseline CDAI • Not eligible for maintenance* • A clinical relapse during the Maintenance Phase[^] • Complete the Maintenance Phase including the Week 66 or Week 74 	
 • Previously enrolled in Study GA29144 and are not eligible or chose not to enroll in Part 1 (OLE) and completed the 12-week SFU • Participated in Part 1 (OLE) and completed the 12-week SFU

CD= Crohn's disease; CDAI =Crohn's Disease Activity Index; FPI=first patient in; OLE=open- label extension; PML=progressive multifocal leukoencephalopathy; Q4W=every 4 weeks; SC=subcutaneous; SM=safety monitoring; SFU = safety follow-up.

*Including patients who completed the Week 14 visit in Study GA29144 and could not subsequently enter the Maintenance Phase, because the sample size was achieved and enrollment into the Maintenance Phase was closed.

**All patients must have completed the 12- week safety follow-up in either GA29144 or GA29145, Part 1 (OLE), as applicable, prior to entering Part 2 (SM).

[^] A clinical relapse during the Maintenance Phase of Study GA29144 is defined as meeting at least one of the following criteria on two consecutive visits (may include unscheduled visits), with at least one of the two consecutive CDAI scores \geq 220: CDAI score \geq the baseline (Week 0) score, or CDAI score \geq 100 points higher than the Week 14 score

Changes to the protocol-planned analyses are described in [Section 4.4](#).

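### Part 2 entry rules conflict for patients who leave the OLE safety follow-up early, and the only Part 2 outcome, a PML incidence, has no planned estimate or confidence limit

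*Protocol*

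**What the plan says.** **Entry to Part 2.** Four places make completion of the 12-week safety follow-up a condition of entry:

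- Protocol Section 4.1.1: "All patients must have completed the 12-week safety follow-up in either GA29144 or GA29145, Part 1 (OLE), as applicable, prior to entering" Part 2. The synopsis repeats this rule.
- Protocol Section 3.1.3: "Regardless of route of entry, patients will enroll following completion of the 12-week safety follow-up period".
- SAP Table 1, for the OLE route: "Participated in Part 1 (OLE) and completed the 12-week SFU".

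Protocol Section 4.4.3 has a paragraph headed "Discontinuation during the 12-Week Safety Follow-Up Period after OLE". It reads "Patients who discontinue the study during the 12-week safety follow-up will be asked to complete the early withdrawal visit" of that follow-up, "and then enter the extended PML monitoring in Part 2 (SM").

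**Analysis of Part 2.** Section 3.3.3 names one outcome, the incidence of PML, suspected or confirmed. Section 6.4 plans a listing with narratives for PML, and narratives for serious adverse events and deaths. Section 6.2 will tabulate how many patients enrol in Part 2 and how many complete or stop early. SAP Sections 1 and 1.1 limit the SAP to Part 1.

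**The concern.** For an OLE patient who leaves the safety follow-up early but would accept telephone monitoring, the protocol gives two opposed instructions. Section 9.2 does not allow waivers of eligibility criteria, so a site cannot follow Section 4.4.3 without breaching Section 4.1.1. Who receives the extended PML monitoring, and who is counted in Part 2, could then differ by site.

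On the analysis side, Part 2 exists to watch for a rare, serious event, and the likeliest result may be no event at all. A listing is then empty, and nothing planned states how large a risk has been excluded. If events do occur, counting rows is unsafe. Section 5.4.6 records each neurological abnormality as a separate adverse event of special interest (AESI), so one patient can contribute several. The population is also mixed. Part 2 takes direct entrants from a placebo-controlled parent study, some of whom may never have had etrolizumab. Section 4.5.2 also sends patients to Part 2 who stopped drug because of confirmed PML.

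**Working it through.** **Entry rule, passages side by side**

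1. *Does the early withdrawal visit count as completion?* No passage says so. Appendix 2, footnote b, describes these patients as leaving before the follow-up is complete.
2. *Does Section 4.1 resolve it?* Its Part 2 population includes "patients from Study GA29145 who either completed or discontinued Part 1 (OLE), and who meet all the eligibility criteria for Part 2 (SM"). That admits discontinuers, but only through the Section 4.1.1 criteria, which leads back to the completion rule.
3. *Does the absence of exclusion criteria for Part 2 (Section 4.1.2) resolve it?* No. It does not cancel an inclusion criterion.
4. *Is the GA29144 route affected?* No. Section 1.3.2, Section 3.1.3, Section 4.1.1 and the Appendix 3 note all require a completed follow-up in GA29144. Section 4.4.3 speaks only of the follow-up after the OLE.
5. *The plan's own figure.* Appendix 3, footnote a, gives 104 weeks of PML monitoring: 12 + 92 = 104, which reproduces. It holds only for those who complete the follow-up. If a patient leaves at week w and the 92 weeks start then (an assumption), the total is w + 92. Leaving at week 6 gives 98 weeks.

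**What an incidence with a confidence limit would show**

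The documents contain no sample size calculation and do not give the Part 2 number. Inputs are the stated ceiling of about 1150 (Section 6.1), an assumed lower number of 400, and complete 92-week follow-up.

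Zero events, exact two-sided 95% upper limit = 1 − 0.025^(1/n):

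| n | Basis | Upper limit |
|---|---|---|
| 1150 | stated ceiling | 0.32% |
| 400 | assumed | 0.92% |
| 1035 | 1150 with 10% placebo-only (assumed) | 0.36% |
| 805 | 1150 with 30% placebo-only (assumed) | 0.46% |

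One event at 1150: 1/1150 = 0.087%, Clopper-Pearson 95% interval 0.002% to 0.48%.

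Optional rate at 1150: patient-years = 1150 × 92 × 7 / 365.25 = 2027.7. The zero-event limit is 3.689 / 2027.7 = 1.8 per 1000 patient-years. At 400 it is 3.689 / 705.3 = 5.2.

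**The case against.** **On entry.** Section 4.4.3 is the only text addressed to exactly these patients, and a specific instruction is often read as governing a general one. Section 4.1, the lack of Part 2 exclusion criteria and the Appendix 3 note, which covers patients who discontinue Part 1, all lean the same way. This stands as mitigation, but it leaves the Section 4.1.1 criterion in force.

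A reader might infer that these patients lose PML surveillance altogether. The documents do not support that. Appendix 2 has the Week 12 assessments, including the PML interview and neurological examination, done at the early withdrawal visit. Sections 5.4.1, 5.7.1 and 5.7.2 ask investigators to report any PML, confirmed or suspected, that they learn of for up to 2 years after the last dose. That reporting is passive, but it limits the consequence. Patients who withdraw consent are not followed under either rule (Section 4.5.1.1).

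**On analysis.** The study is descriptive, and even in Part 1 the SAP plans confidence intervals only for rate tables of selected events, not for proportions (SAP 4.2.2). That is fair: the added table is an improvement, not the repair of an error in a test. It is still what reporting an incidence calls for, and it involves no test.

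Three stronger readings should be resisted:

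- *That no incidence can be formed.* Listed cases over the enrolment count in Section 6.2 give a crude one.
- *That a rate per patient-year is missing.* Section 3.3.2 names such a rate for infections and malignancies. Section 3.3.3 does not for PML, so a rate goes beyond the stated outcome.
- *That the SAP wrongly omits Part 2.* It excludes Part 2 by declared scope. Whether a separate Part 2 plan exists cannot be known from these documents.

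**Conclusion.** Both halves hold on the text.

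The entry rules contradict each other for one narrow group: OLE-route patients who leave the 12-week follow-up early and would still take part in Part 2. The number is not given and is probably small, and passive reporting softens the consequence. It remains a written conflict that a site cannot resolve alone. It does not extend to direct entrants from GA29144.

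The sole Part 2 outcome is named as an incidence, yet the plan defines no estimate, no etrolizumab-exposed denominator and no confidence limit.

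The limits of 0.32% and 0.92% are illustrations that assume zero events and complete follow-up. A reader might take the gap between them as the size of a flaw. It is not: it reflects only that the Part 2 number is unknown here. With the number fixed at 1150, an assumed 10% to 30% placebo-only share moves the limit modestly, to between 0.36% and 0.46%. No Part 1 result is touched.

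**What to change.** **1. Entry.** Reconcile the synopsis, Sections 3.1.3, 4.1.1 and 4.4.3, and SAP Table 1 so that one rule governs patients who leave the OLE safety follow-up early. Which rule is for the sponsor to decide.

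**2. Analysis.** Keep the narratives and add one table to Section 6.4:

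- Patients with at least one new confirmed PML event and, separately, patients with at least one new suspected PML event, over etrolizumab-exposed Part 2 entrants, each with an exact 95% confidence interval.
- Events counted from Part 2 entry to the last PML contact. This matches the scope of Section 6.4. If the optional patient-year rate is added, it also avoids reusing the 12 follow-up weeks already in the Part 1 patient-years (SAP 4.2.2).
- Patients with PML confirmed before entry listed, but left out of the at-risk count.
- Placebo-only direct entrants shown separately.
- Suspected PML counted once per patient from the PML-related AESI and serious adverse event records (Sections 5.4.2 and 5.4.6). The Appendix 8 form item on whether PML is suspected should be used only if that form is confirmed to be collected in Part 2. Section 5.4.2 limits the Part 2 case report form to PML-related AESIs and serious adverse events.

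**Cost.** Wording changes in the protocol and SAP Table 1, one extra table, and exposure status for direct entrants from Study GA29144. No new visits are needed.
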